## **Lesions with Prior Local Treatment**

Tumor lesions situated in a previous irradiated area or in an area subjected to other locoregional therapy are usually not considered measurable unless there has been demonstrated progression in the lesion.

## **Target Lesions**

All measurable lesions up to a maximum of two lesions per organ and five lesions in total, representative of all involved organs, should be identified as target lesions and recorded and measured at baseline. Target lesions should be selected on the basis of their size (lesions with the longest diameter) and their suitability for accurate repeated measurements (either by imaging techniques or clinically). A sum of the longest diameter (LD) for all target lesions will be calculated and reported as the baseline sum LD. The baseline sum LD will be used as reference by which to characterize the objective tumor response.

## **Non target Lesions**

RECIST criteria require unequivocal quantification of the changes in tumor size for adequate interpretation of the sum of target lesions. Consequently, when the boundaries of the primary are difficult to delineate, this tumor should not be considered a target lesion.

## **Guidelines for Evaluation of Measurable Disease**

The same method of assessment and the same technique should be used to characterize each identified and reported lesion at baseline and during follow-up. Imaging-based evaluation is preferred to evaluation by clinical examination when both methods have been used to assess the antitumor effect of a treatment.

### Evaluation of Target Lesions

Complete Response	Disappearance of all target lesions. Any pathological lymph nodes (whether target or nontarget) must have reduction in short axis to <10 mm.
Partial Response	At least a 30% decrease in the sum of the LD of target lesions, taking as reference the baseline sum LD.
Stable Disease	Neither sufficient shrinkage to qualify for partial response nor sufficient increase to qualify for progressive disease (PD), taking as reference the smallest sum LD since the treatment started.
Progressive Disease	At least a 20% increase in the sum of the LD of target lesions, taking as reference the smallest sum on study (this includes the baseline sum if that is the smallest on study). In addition to the relative increase of 20%, the sum must also demonstrate an absolute increase of at least 5 mm. The appearance of one or more new lesions is also considered progression.

### Evaluation of Nontarget Lesions

Complete Response	Disappearance of all nontarget lesions and normalization of tumor marker level.
Stable Disease/Incomplete Response	Persistence of one or more nontarget lesion(s) or/and maintenance of tumor marker level above the normal limits.
Progressive Disease	Appearance of one or more new lesions and/or unequivocal progression of existing nontarget lesions.

If tumor markers are initially above the institutional ULN, they must normalize for a patient to be considered a complete responder.

### Evaluation of Best Overall Response

The best overall response is the best response recorded from the start of the treatment until disease progression/recurrence (taking as reference for PD the smallest measurements recorded since the treatment started). The patient's best response assignment will depend on the achievement of both measurement and confirmation criteria.

Evaluation of Best Overall Response			
Target Lesions	Nontarget Lesions	New Lesions	Overall Response
CR	CR	No	CR
CR	Non-CR/non-PD	No	PR
CR	Not evaluated	No	PR
PR	Non-PD or not evaluated	No	PR
SD	Non-PD or not evaluated	No	SD

Evaluation of Best Overall Response			
Target Lesions	Nontarget Lesions	New Lesions	Overall Response
Not Evaluated	Non-PD	No	NE
PD	Any	Yes or No	PD
Any	PD	Yes or No	PD
Any	Any	Yes	PD
NE = Not evaluable.			

Patients with a global deterioration of health status requiring discontinuation of treatment without objective evidence of disease progression at that time should be classified as having symptomatic deterioration. Every effort should be made to document the objective progression, even after discontinuation of treatment.

In some circumstances, it may be difficult to distinguish residual disease from normal tissue. When the evaluation of complete response (CR) depends on this determination, it is recommended that the residual lesion be investigated (fine needle aspiration/biopsy) prior to confirming the CR status.

### **Confirmatory Measurement/Duration of Response**

#### Confirmation

CT scans are required at screening and at the end of every 3rd cycle of treatment.

#### Duration of Overall Response

The duration of overall response is measured from the time measurement criteria are met for CR or PR (whichever is first recorded) until the first date that recurrent or PD is objectively documented (taking as reference for PD the smallest measurements recorded since the treatment started).

The duration of overall CR is measured from the time measurement criteria are first met for CR until the first date that recurrent disease is objectively documented.

#### Duration of Stable Disease

SD is measured from the start of the treatment until the criteria for progression are met, taking as reference the smallest measurements recorded since the treatment started.

## 15.3 Appendix C

### Modified Gynecological Cancer Intergroup (GCIIG) Guidelines

#### *GCIIG Guidelines for Response Using CA-125* (adapted for use in this trial)

GCIIG CA-125 definitions are available at <http://gcig.igcs.org/CA-125.html>.

To be evaluable for response by CA-125 requires at least one pre-treatment sample  $>2 \times$  ULN and two post-treatment samples confirming a response

A response to CA-125 has occurred if there is at least a 50% decrease as the result of the treatment. The pre / post treatment samples must satisfy the following criteria:

1. There must be at least one sample that is  $>2 \times$  ULN prior to initiation of treatment
2. The second sample (post-treatment) must be  $\leq 50\%$  of the pre-treatment sample;
3. The confirmatory third sample must be  $\geq 21$  days after the second sample and  $\leq 110\%$  of the second sample;
4. Any intervening samples between samples 2 and 3 must be  $\leq 110\%$  of the previous sample unless considered to be increasing because of tumor lysis.

Per inclusion criteria #5, CA-125 must be  $<ULN$  prior to study entry. This requirement applies to all patients, including those who achieved a best response of PR by serologic CA-125 response criteria. Thus, patients must have achieved a  $>50\%$  reduction in CA-125 level and also have CA-125  $<ULN$ .

Patients are not evaluable by CA-125 if they have received mouse antibodies or if there has been medical or surgical interference with their peritoneum or pleura during the previous 28 days.

## 15.4 Appendix D

### Eastern Cooperative Oncology Group (ECOG) Performance Status Scale

ECOG Performance Status	
0	Fully active, able to carry on all predisease performance without restriction.
1	Restricted in physically strenuous activity but ambulatory and able to carry out work of a light or sedentary nature (eg, light house work or office work).
2	Ambulatory and capable of all self care but unable to carry out any work activities. Up and about more than 50% of waking hours.
3	Capable of only limited self care; confined to bed or chair more than 50% of waking hours.
4	Completely disabled. Cannot carry on any self care. Totally confined to bed or chair.
5	Dead.

In the event performance status is assessed by the Karnofsky Performance Status scale, the following conversion chart applies.

Karnofsky Performance Status			ECOG Performance Status
General Description	Score	Specific Description	Score
Able to carry on normal activity and to work; no special care needed	100	Normal; no complaints; no evidence of disease	0
	90	Able to carry on normal activity; minor signs or symptoms of disease	1
	80	Normal activity with effort; some signs or symptoms of disease	
Unable to work; able to live at home and care for most personal needs; varying amount of assistance needed	70	Cares for self, unable to carry on normal activity or to do active work	2
	60	Requires occasional assistance, but is able to care for most of personal needs	
	50	Requires considerable assistance and frequent medical care	3

Karnofsky Performance Status			ECOG Performance Status
General Description	Score	Specific Description	Score
Unable to care for self; requires equivalent of institutional or hospital care; disease may be progressing rapidly	40	Disabled; requires special care and assistance	4
	30	Severely disabled; hospital admission is indicated although death not imminent	
	20	Very sick; hospital admission necessary; active supportive treatment necessary	
	10	Moribund; fatal processes progressing rapidly	
	0	Dead	
			5

## 15.5 Appendix E

### **National Comprehensive Cancer Network – Functional Assessment of Cancer Therapy (NCCN-FACT) FACT - Ovarian Symptom Index (FOSI-18) instrument (NCCN-FACT FOSI-18) – English Version**

Sample form and background available at: <http://www.facit.org/FACITOrg/Questionnaires>.

Patients will complete the instrument on an electronic device. This device is a Class 1 listed (i.e., approved) device.

Below is a list of statements that other people with your illness have said are important.

**Please circle or mark one number per line to indicate your response as it applies to the past 7 days.**

		Not at all	A little bit	Some-what	Quite a bit	Very much	
D R S- P	GP1	I have a lack of energy	0	1	2	3	4
	GP4	I have pain	0	1	2	3	4
	GP6	I feel ill	0	1	2	3	4
	O3	I have cramps in my stomach area	0	1	2	3	4
	HI7	I feel fatigued	0	1	2	3	4
	Cx6	I am bothered by constipation	0	1	2	3	4
	O1	I have swelling in my stomach area	0	1	2	3	4
D R S- E	C3	I have control of my bowels	0	1	2	3	4
	GF5	I am sleeping well	0	1	2	3	4
	GE6	I worry that my condition will get worse	0	1	2	3	4
	GP2	I have nausea	0	1	2	3	4
T S E	B5	I am bothered by hair loss	0	1	2	3	4
	GP5	I am bothered by side effects of treatment	0	1	2	3	4
	O2	I have been vomiting	0	1	2	3	4
F W B	BMT15	I am bothered by skin problems	0	1	2	3	4
	BMT5	I am able to get around by myself	0	1	2	3	4
	GF3	I am able to enjoy life	0	1	2	3	4

GF7	I am content with the quality of my life right now .....	0	1	2	3	4
-----	--	---	---	---	---	---

### **Euro-QoL5D (EQ-5D) – English Version for the US**

By placing a checkmark in one box in each group below, please indicate which statements best describe your own health state today.

#### **Mobility**

- I have no problems in walking about
- I have some problems in walking about
- I am confined to bed

#### **Self-Care**

- I have no problems with self-care
- I have some problems washing or dressing myself
- I am unable to wash or dress myself

#### **Usual Activities** (*e.g. work, study, housework, family or leisure activities*)

- I have no problems with performing my usual activities
- I have some problems with performing my usual activities
- I am unable to perform my usual activities

#### **Pain/Discomfort**

- I have no pain or discomfort
- I have moderate pain or discomfort
- I have extreme pain or discomfort

#### **Anxiety/Depression**

- I am not anxious or depressed

[figure not shown]
I am moderately anxious or depressed

I am extremely anxious or depressed

To help people say how good or bad a health state is, we have drawn a scale (rather like a thermometer) on which the best state you can imagine is marked 100 and the worst state you can imagine is marked 0.

We would like you to indicate on this scale how good or bad your own health is today, in your opinion. Please do this by drawing a line from the box below to whichever point on the scale indicates how good or bad your health state is today.

**Your own  
health state  
today**

## 15.6 Appendix F

### Examples of CYP Substrates with Narrow Therapeutic Range

CYP Enzyme	Substrates with Narrow Therapeutic Range a
CYP1A2	Tizanidine, theophylline
CYP2C9	Warfarin, phenytoin
CYP3A	Alfentanil, astemizole, cisapride, cyclosporine, dihydroergotamine, ergotamine, fentanyl, pimozide, quinidine, sirolimus, tacrolimus, terfenadine

The table is based on the Draft FDA Guidance on Drug Interaction Studies — Study Design, Data Analysis, Implications for Dosing, and Labeling Recommendations, 2012.

a CYP substrates with narrow therapeutic range refers to drugs whose exposure-response relationship indicates that small increases in their exposure levels by the concomitant use of CYP inhibitors may lead to serious safety concerns (eg, Torsades de Pointes).

WHO	World Health Organization

Analysis Population Definitions

tBRCA	Patients with BRCA mutation in their tumor
HRD	Patients with HRD ⁺ tumors (a NGS HRD assay result), composed of
	tBRCA and non-tBRCA LOH+
non-tBRCA LOH+	Patients without a tBRCA mutation and with percent of tumor genome
	$LOH \ge 16\%$
non-tBRCA LOH-	Patients without a tBRCA mutation and with percent of tumor genome
	LOH < 16%
non-tBRCA LOH unknown	Patients who do not have a tBRCA mutation and where the LOH result is
	unknown.
Intent-to-Treat (ITT)	All randomized patients
Safety Population	The safety population will consist of all patients who received at least one
	dose of protocol-specified treatment

1 INTRODUCTION

This document describes the statistical analyses and data presentations to be performed for the clinical study report (CSR) of Clovis Oncology protocol CO-338-014 "A Multicenter, Randomized, Double-Blind, Placebo-Controlled Phase 3 Study of Rucaparib as Switch Maintenance Following Platinum-Based Chemotherapy in Patients with Platinum-Sensitive, High-Grade Serous or Endometrioid Epithelial Ovarian, Primary Peritoneal or Fallopian Tube Cancer."

This statistical analysis plan (SAP) provides a comprehensive and detailed description of the strategy, rationale, and statistical techniques to be used to assess the efficacy and safety of rucaparib (CO-338) compared with placebo in patients with platinum-sensitive high-grade serous ovarian or endometrioid epithelial ovarian, primary peritoneal, or fallopian tube cancer who achieved a response to platinum-based therapy.

The purpose of the SAP is to ensure the credibility of the study findings by specifying the statistical approaches to the analysis of study data prior to snapshot and unblinding of treatment codes. This SAP provides additional details around the statistical analyses that are outlined in the original protocol dated 9 Sep 2013, and three protocol amendments (Amendment 1 dated 4 Nov 2014, Amendment 2 dated 9 Mar 2015, and Amendment 3 dated 7 Jul 2016).

All statistical analyses detailed in this SAP will be conducted using SAS[®] Version 9.3 or higher.

2 OVERALL STUDY DESIGN, OBJECTIVES, AND ENDPOINTS

2.1 Study Objectives and Endpoints Outlined in Original Protocol

Table 1. Primary, Secondary, and Exploratory Objectives and Endpoints

Primary Objectives	Primary Endpoints
To evaluate progression-free survival (PFS) by Response Evaluation Criteria in Solid Tumors (RECIST) Version 1.1, as assessed by the investigator (invPFS), in molecularly-defined homologous recombination deficiency (HRD) subgroups	Disease progression according to RECIST v.1, as assessed by the investigator (invPFS), or death from any cause, in molecularly- defined HRD subgroups
Secondary Objectives	Secondary Endpoints
To evaluate PFS by RECIST, as assessed by independent radiology review (IRR), in molecularly-defined HRD subgroups	Disease progression according to RECIST v1.1, as assessed by independent radiology review (irrPFS), or death from any cause, in molecularly-defined HRD subgroups
To evaluate patient-reported outcome (PRO) of disease-related symptoms utilizing the disease- related symptoms – physical (DRS-P) subscale of the National Comprehensive Cancer Network-Functional Assessment of Cancer Therapy (NCCN-FACT) FACT-Ovarian Symptom Index 18 (FOSI-18)	Time to a 4-point decrease in the DRS–P subscale of the FOSI-18
To evaluate PRO utilizing the complete FOSI- 18 instrument	Time to a 8-point decrease in the total score of the FOSI-18
To evaluate survival benefit	Overall survival (OS)
To evaluate safety	The incidence of adverse events (AEs), clinical laboratory abnormalities, and dose modifications
To determine the population pharmacokinetics (PK) of rucaparib	Individual model parameter estimates of rucaparib and covariates identification
Exploratory Objectives	Exploratory Endpoints
To evaluate the relationship between cancer antigen 125 (CA-125) levels and invPFS	Association between the change from baseline in CA-125 measurements and invPFS
To evaluate PFS2 (PFS on the subsequent line of treatment)	Time to the next event of disease progression or death, as assessed by the investigator
To evaluate overall response rate (ORR)	ORR per RECIST v1.1, as assessed by both the investigator and IRR, in patients who have measureable disease at study entry

Table 1 continued.	Primary, Secondary, and Exploratory Objectives and
	Endpoints

•	
To evaluate duration of response (DOR)	DOR per RECIST v1.1, as assessed by both the investigator and IRR
To evaluate PRO utilizing the Euro-QoL 5D (EQ-5D) instrument	PRO as measured by the total score on the EQ-5D
To explore the relationship between rucaparib exposure, efficacy, and safety	Rucaparib PK, invPFS, irrPFS, CA-125, AEs, clinical laboratory abnormalities, and dose modifications

2.2 Trial Design

This double-blind, randomized, multicenter, Phase 3 study will compare rucaparib with placebo in patients with platinum-sensitive, high-grade serous or endometrioid epithelial ovarian, primary peritoneal, or fallopian tube cancer who have achieved a response to platinum-based therapy (ARIEL3).

The initial clinical trial assay (CTA) will be utilized to stratify patients for randomization at study entry into 1 of 3 HRD subgroups (tBRCA, nbHRD, and biomarker negative). The CTA sequences DNA extracted from tumor tissue and identifies mutations in 30 genes involved in HRD: *BRCA1/2* (stratify into the tBRCA) and 28 other HRR genes (stratify into nbHRD) (see Appendix A for the specific list of genes). Patients with no mutations identified in the 30 HRD genes are stratified into the biomarker negative subgroup. Eligible patients will be randomized (2:1) using Interactive Response Technology to receive either rucaparib or placebo.

The primary efficacy endpoint for this study is to evaluate PFS, as assessed by the investigator, in molecularly-defined HRD subgroups. Investigational centers will interpret tumor scans locally for the purpose of making treatment decisions. IRR will also be performed to support analyses by investigator assessment. Secondary endpoints include patient-reported outcome as assessed by the FOSI-18 instrument using an electronic PRO tool and overall survival.

For the efficacy analyses, patients will be assigned to molecularly-defined HRD subgroups based on the CTA results. Results from study CO-338-017 (ARIEL2) Part 1 demonstrated that genomic loss of heterozygosity (LOH) was a good predictor of rucaparib sensitivity. Based on these ARIEL2 results, an optimized rucaparib sensitivity algorithm, which includes a pre-specified LOH cut-off of 16% percent genomic LOH along with tBRCA mutation status, has been established and documented, and will be prospectively applied to the primary analysis of ARIEL3 That is, all analyses will be performed using the optimized definition of HRD. Section 3.2 details the full development for the LOH cut-off used for HRD classification of all patients without a tBRCA mutation for the purpose of ARIEL3 efficacy analyses.

A separate analysis plan will be created for the clinical validation of the companion diagnostic (CDx) test. This report will evaluate the primary endpoint of invPFS based on the CDx results and will also compare the CTA and CDx results. A multiple imputation analysis will also be performed in order to evaluate the effect of patients with an unknown CDx result.

Safety analyses are based on adverse event, vital signs, and physical exam collection and central laboratories measurements.

2.3 Sample Size

Approximately 540 patients will be randomized (2:1) to receive either rucaparib or placebo in this study. A minimum of 180 and a maximum of 200 patients with a deleterious tBRCA mutation will be enrolled. Enrollment of patients with a known deleterious germline *BRCA1/2* mutation (gBRCA) documented in their medical record will not exceed 150. There is no minimum number of patients required for each of the nbHRD and biomarker negative subgroups; however, no more than 360 total patients will be randomized for stratification into these subgroups combined.

Tumor HRD status by the CTA (see Section 3.2) will be determined after randomization, but before the final efficacy analysis, so that the primary endpoint (PFS in molecularly-defined HRD subgroups) can be assessed prospectively.

Group	Hazard Ratio	Cumulative N	Minimum Number of Events (70%)	Median PFS Placebo vs Rucaparib (months)	Power	One- sided Alpha
tBRCA	0.50	180	126	6 vs 12	90%	0.025
HRD	0.60	300	210	6 vs 10	90%	0.025
ITT	0.70	540	378	6 vs 8.5	90%	0.025

The study will end after 70% of the patients in the tBRCA subgroup have an observed event of investigator-determined disease progression or death. If the minimum number of tBRCA patients are enrolled, then the study will end following the 126th event of investigator-determined disease progression or death. Similarly, if the maximum number of tBRCA patients are enrolled then the study will end following the 140th event of investigator-determined disease progression or death. The Independent Data Monitoring Committee (IDMC) will inform the sponsor when the required number of PFS events have been observed in order to ensure the sponsor remains blinded to which patients are in the tBRCA subgroup.

2.4 Data Cut-off Used

The IDMC will inform the sponsor when the required number of PFS events have been observed and when treatment blind can be broken for the study. All data up to and including this date will be cleaned and collected before the treatment blind can be broken. In addition, key vendor data such as HRD classification from the Foundation Medicine CTA, central laboratory measurements, and Independent Radiology Review up to this date will also need to be collected. This process can take up to 4-8 weeks after the established visit cut-off for the primary analysis. The dataset will include all data that are collected and dated prior to or on the date of the visit cut-off date.

3 GENERAL ANALYSIS CONVENTIONS

The summary tables will be presented by randomized treatment group (rucaparib vs placebo) within the nested populations outlined in the step-down procedure in Section 3.2 and other subgroups of interest.

Quantitative variables will typically be summarized using frequencies and percentages for appropriate categorizations and may also be summarized using descriptive statistics. For variables summarized with descriptive statistics, the following will be presented: N, mean, standard deviation, median, minimum, and maximum. Categorical variables will be presented using frequencies and percentages. The Kaplan-Meier methodology will be used to summarize time-to-event variables. If estimable, the 25th, 50th (median), and 75th percentiles will be presented along with the Kaplan-Meier estimates of event rates at 6-month intervals. The number of patients with events and the number of censored patients will also be presented. The stratified log rank test will be used to compare the PFS distributions between the randomized treatment groups. In addition, the Cox proportional hazards model will be used to estimate the hazard ratio between the randomized treatment groups. Months will be calculated as number of days divided by 30.4375.

All data will be used to their maximum possible extent, but without any imputations for missing data.

Unless otherwise indicated, baseline is defined as the last measurement on or prior to randomization.

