3.1 Populations Definitions

Intent-to-Treat Population: The intent-to-treat (ITT) population will consist of all randomized patients.

Safety Population: The safety population will consist of all patients who received at least one dose of protocol-specified treatment.

In addition to the population definitions above, further analysis subgroups within the ITT population based on tumor HRD status by the CTA are outlined in Section 3.2 below.

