5 PROTOCOL DEVIATIONS

Major protocol deviations will be identified via use of both central lab data and EDC data. The categories for major protocol deviations are in accordance with the ICH E3 guidelines¹ and will be identified prior to database lock. The deviations that will be deemed major fall under the following categories:

- Incorrect IP treatment compared to randomization
- Inclusion or exclusion criteria deviations
- Over-dose or under-dose of study drug
- Prohibited medications such as other anti-cancer medications
- Any other significant deviation that had the potential to affect the primary efficacy or safety of the patients

A listing with all the major protocol deviations will be presented.

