8 PRIOR AND CONCOMITANT MEDICATIONS

All concomitant treatments documented during the study period will be summarized in frequency tabulations for each randomized treatment group and overall. Prior/concomitant medication coding will utilize the World Health Organization (WHO) Drug Dictionary version 2016SEP01DDE (Enhanced).

Prior medications will only be presented in listings. Prior medications will be defined as those medications with both a start and a stop date that is before the day of the first dose of study drug administration. If either the start date and/or the stop date of the medication is missing so that it is unclear whether the medication was stopped prior to first dose of study drug administration then the medication will be included in the summary of the concomitant medications.

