12 SAFETY ANALYSIS

The safety analyses will be performed using the safety population.

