12.2 Clinical Laboratory Evaluations

Clinical laboratory evaluations include the continuous variables for hematology, serum chemistry, and urinalysis. The laboratory values will be presented in SI units. The on-treatment period will be defined as the time from randomization to 28 days after the last dose of study drug. Laboratory values collected during the on-treatment period will be included in the summary tables. The laboratory values collected after the on-treatment period will only be presented in the data listings.

The summary of laboratory data will include descriptive statistics (N, mean, SD, minimum, median, and maximum) of the maximum, minimum, and last value during the on-treatment period. Summaries using descriptive statistics of the change from baseline to the maximum, minimum, and last value during the on-treatment period will also be given.

Summary tables from baseline to the maximum on-treatment toxicity grade (CTCAE Version 4.03) for each lab parameter will be summarized. In addition, the number and percent of patients who has at least one worsening in toxicity grade on-treatment compared to baseline toxicity grade will be summarized by treatment group.

Laboratory data including normal ranges and flagged abnormal laboratory findings will be provided using by-patient listings.

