12.3 Vital Signs

The on-treatment period will be defined as the time from randomization to 28 days after the last dose of study drug. Vital sign measurements collected during the on-treatment period will be included in the summary tables. The vital sign measurements collected after the on-treatment period will only be presented in the data listings.

The summary of vital sign data will include descriptive statistics (N, mean, SD, minimum, median, third quartile and maximum) of the maximum, minimum and last value during the on-treatment period. Summaries using descriptive statistics (N, mean, SD, minimum, median, and maximum) of the change from baseline to the maximum, minimum, and last value during the on-treatment period will also be given. The data will be presented separately for each randomized treatment group, and overall.

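### Safety tables follow the randomized arm, with no rule for counting a patient who received the wrong product under the treatment actually taken

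*SAP*

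**What the plan says.** **Grouping.** SAP section 3 gives the general rule: "The summary tables will be presented by randomized treatment group (rucaparib vs placebo". The sentence goes on to place these tables within the nested populations and other subgroups of interest. Three later sections touch on grouping:

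- Section 8 has concomitant treatments "summarized in frequency tabulations for each randomized treatment group and overall".
- Section 12.2 says that laboratory grade worsening "will be summarized by treatment group", without saying whether that means randomized or actual treatment.
- Section 12.3 says of vital signs: "The data will be presented separately for each randomized treatment group, and overall".

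Sections 7 (exposure) and 12.1 (adverse events) name no grouping.

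**Population.** Section 12 states: "The safety analyses will be performed using the safety population". Section 3.1 defines that population: "The safety population will consist of all patients who received at least one dose of protocol-specified treatment". Protocol section 11.1 has the same definition. It settles who is included but not the column in which they are counted.

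**Wrong product.** The first category of major deviation in SAP section 5 is "Incorrect IP treatment compared to randomization". The output planned for these deviations is: "A listing with all the major protocol deviations will be presented". Neither document says that such a patient is tabulated under the product taken.

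**The concern.** Grouping by randomized arm protects the efficacy comparison. A safety table has a different job: to show what happened to patients exposed to each product. Under the stated rule, a placebo-randomized patient who took rucaparib contributes any rucaparib toxicity to the placebo column. A rucaparib-randomized patient who took placebo dilutes the rucaparib column. For events that the drug causes, both errors on average bring the arms closer together, which is the less cautious direction for a safety analysis. The exposure is greatest where counts are low: rare events, and the smaller groups in SAP section 12.4 (tBRCA, and germline and somatic within it).

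**Working it through.** The plan gives no figure on this point, so there is none to reproduce. The check has a textual part and an illustration of size.

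**1. Which rule governs adverse events?** Section 12.1 is silent, so the answer rests on the general rule in section 3. Its mention of nested populations could suggest efficacy tables only. Two passages speak against that: section 12.3 applies randomized grouping to safety data outright, and section 12.4 uses the nested tBRCA and HRD populations for safety. With no as-treated statement anywhere, randomized grouping is the only rule a programmer could apply.

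**2. Inputs.**
- From SAP section 2.3: about 540 patients, 2:1, so 540 × 2/3 = 360 rucaparib and 540 × 1/3 = 180 placebo. The tBRCA minimum is 180, so about 180 × 1/3 = 60 placebo.
- Assumed: everyone randomized is dosed, and a misdosed patient takes the wrong product throughout.
- Assumed event risks, rucaparib/placebo (pR/pP): 20/1%, 50/15%, 80/40%.
- The documents give no count of misdosed patients. Let k be placebo-randomized patients given rucaparib, and m the reverse.

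**3. Expected bias.** The as-randomized rates are

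- rucaparib column: [(360 − m)·pR + m·pP] / 360
- placebo column: [(180 − k)·pP + k·pR] / 180

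Subtracting, the expected difference shrinks by (pR − pP) × (m/360 + k/180). For k = 1, m = 0 and 50/15%: 0.35/180 = 0.19 points, so a true 35.0 appears as 34.8.

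Shrinkage in percentage points:

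| k, m | 20/1% | 50/15% | 80/40% |
|---|---|---|---|
| 0, 0 | 0 | 0 | 0 |
| 1, 0 | 0.11 | 0.19 | 0.22 |
| 0, 1 | 0.05 | 0.10 | 0.11 |
| 2, 2 | 0.32 | 0.58 | 0.67 |
| 5, 5 | 0.79 | 1.46 | 1.67 |
| 5, 10 | 1.06 | 1.94 | 2.22 |

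**4. Largest effect of one patient.** If the patient has the event, the column rate moves by at most 1/180 = 0.56 points (placebo) or 1/360 = 0.28 points (rucaparib). In tBRCA the placebo maximum is 1/60 = 1.7 points, and the expected shift per placebo patient given rucaparib is 0.19/60 = 0.32 to 0.40/60 = 0.67 points.

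**5. Direction in a single data set.** Take observed as-randomized counts of 180/360 and 27/180, a difference of 50.0 − 15.0 = 35.0 points, with one placebo-randomized patient actually on rucaparib.

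- That patient had no event: as treated, 180/361 − 27/179 = 49.9 − 15.1 = 34.8. Randomized grouping slightly widens the difference.
- That patient had the event: as treated, 181/361 − 26/179 = 50.1 − 14.5 = 35.6. Randomized grouping narrows it.

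Understatement is therefore a tendency on average, not a certainty.

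**The case against.** The best defence is that this is a wording gap with no demonstrated consequence. The section 5 category is one of a generic set aligned with ICH E3. Protocol sections 7.3 and 7.5 describe real controls: the interactive system assigns bottles by randomization and must be consulted at every dispensation, with real-time entry at sites. No misdosed patient is documented. The deviation listing would let a reader find one, and adverse events of special interest are reported individually under protocol sections 10.3 and 10.8. All of this stands, and it limits the size. It does not remove the point, because a listing identifies a patient without correcting the table.

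A reader might infer more than the documents support:

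- **That the SAP expects wrong dosing.** A deviation category provides for an event; it does not predict one.
- **That the SAP explicitly orders adverse events by randomized arm.** Section 12.1 does not say so; the general rule supplies it.
- **That five misdosed placebo patients would shift the placebo rate by 5/180 = 2.8 points.** That requires all five to have the event and none to have had it on placebo. Under the assumed risks the expected figure is 5 × 0.11 to 5 × 0.22, about 0.5 to 1.1 points.
- **That the bias always runs toward no difference.** Step 5 gives a counterexample.
- **That one rare case would decide a planned comparison.** SAP section 12 specifies no between-arm test of adverse events and no special-interest table. One case could still change how a table with very low counts reads.

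A further fair objection concerns the remedy. Drug is dispensed visit by visit, so a single wrong bottle is a plausible error. Counting a patient under rucaparib after any rucaparib dose could charge to rucaparib events that came before it. The convention therefore needs care.

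**Conclusion.** The gap is real. The only grouping rule that reaches the safety tables is by randomized arm, while the population is defined by dosing and a wrong-product category is handled by a listing alone. The numerical effect depends on facts the documents do not give. It is zero with no misdosing. Otherwise it is about 0.1 to 0.2 points in the between-arm difference per placebo patient given rucaparib throughout, and about half that per rucaparib patient given placebo, under the assumed risks and full dosing of 360 and 180 patients. Common events would hardly change unless several patients were affected; rare events and the small safety subgroups are more sensitive. The point does not affect the efficacy analysis and does not show that any harm has been concealed. It merits correction because treatment received is the standard and less biased grouping for safety and costs little.

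**What to change.** In SAP sections 3.1 and 12, state that safety, exposure and laboratory tables are grouped by treatment actually received, and keep the randomized arm for efficacy. Make section 12.3 agree, and replace the undefined term in section 12.2.

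Pre-specify one convention for patients who took both products. Two workable choices are:

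- any rucaparib dose counts as rucaparib, with events before the first rucaparib dose flagged; or
- the patient is counted under the product taken for most of the exposure.

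Footnote each table with the number of patients reassigned, even if it is zero. If no patient received the wrong product, that statement closes the point.

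The cost is one sentence, one derived variable and a somewhat arbitrary rule for mixed exposure. No new data are needed. The change can still be applied to later safety output, since serious and special-interest events continue to be recorded under protocol section 10.7.
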